The Combined Portfolio Diet and Exercise Study (PortfolioEx)

NCT 02481466

Protocol - September 2, 2022

Name of Nominated Principal Applicant	(V21) September 2, 2022
[name]	
Full project title	
MRI – Enhanced Dietary Portfolio plus Exercise on Cardiovascular Risk	

Combined Study Protocol

Protocol

12B) PROPOSED TRIAL

12B) I. What is the proposed trial design? This is a randomized 2x2 factorial design with four experimental arms of 3 years duration (Figure 2) to estimate the effect of the enhanced dietary portfolio, with or without increased physical activity under real world conditions. Participants will be recruited in 3 academic centers in 3 cities across Canada (Quebec, Toronto, Vancouver) from newspaper advertisements providing they do not require pharmacological intervention according to current CCS guidelines (1) and are within 30% of their target LDL-C concentrations for the low or moderate risk category according to current Canadian Working Group recommendations (2), i.e. those who would normally be considered for initial treatment with lifestyle alone. All participants will first be screened by ultrasound for the presence of plaque in the carotid arteries and will then be randomized to one of the four experimental arms:

[figure not shown]
- 1) enhanced dietary portfolio (Appendix 4- Table 1) and an intensive increased physical activity program with follow up at 3-month intervals for the remainder of the trial,
- 2) enhanced dietary portfolio and a copy of Health Canada Physical Activity Guidelines with advice to increase physical activity
- 3) control diet (modified DASH, Appendix 4- Table 2) given as routine clinical advice as used in our recent studies (JAMA 2008, 2011) (3, 4) and an intensive increased physical activity program with follow up at 3 month intervals for the remainder of the trial
- 4) control diet (modified DASH) as described in (3) above and a copy of Health Canada Physical Activity Guidelines with advice to increase physical activity.

[name]

Full project title

MRI – Enhanced Dietary Portfolio plus Exercise on Cardiovascular Risk**Combined Study Protocol**

Figure 2: Schematic Design of Combined Study

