We have selected -106.5mm^3 as the effect size treatment difference at year 3 in MRI assessed plaque volume based on a study by Migrino et al. that demonstrated a reduction in plaque volume following increased statin dosage (36). This study demonstrated a 60mm^3 reduction in plaque volume for a 0.31mmol reduction in LDL-C (36) over a 6-month period. Our own recent portfolio study (**JAMA 2011**) demonstrated a 0.49mmol/L LDL-C reduction at 6 months on the portfolio arm after allowance was made for 0.16mmol/L LDL-C reduction on the control. Our planned study will last for 3 years and our unpublished open label single phase dietary portfolio study of 61 participants indicated a further reduction of 0.06mmol/L in LDL-C over the 6 month to 3 year period. We have added this further reduction to our JAMA 2011 value (4), giving an overall 0.55mmol/L LDL-C reduction. This 0.55mmol/L LDL-C reduction would correspond to a between treatment difference of 106.5mm^3 in plaque volume, according to the findings of Migrino and colleagues and therefore will be our effect size (36).

ii) SD was determined to be 276mm^3 by using a pooled SD from the Migrino paper (baseline: 300mm^3 , end of treatment: 331m m^3 , $n=26$) (36), a [name] cross-sectional assessment (210mm^3 , $n=10$) (37), and our own preliminary data from our CIHR diabetes study at baseline and 1 year (baseline: 227mm^3 , 1-year: 225mm^3 , $n=16$) (pooled data, blinded to treatment). We used the two papers since they assessed individuals with more modest plaque, similar to the population to be recruited. These SDs spanned the range of SDs emerging from our current CIHR funded glycemic index MRI study.

iii) Dropout: Our recent portfolio diet study had a dropout rate of 23% (**JAMA 2011**) (4). However, our current CIHR funded low GI diet study with similar ultrasound and MRI protocol has only had a 10% (7/69) dropout in the 1-year period (6/7 dropped out in the first 3 months). We therefore consider our dropout rate will be between 10% and 25% and most likely below 20% (i.e. >80% retention), which has traditionally been considered as providing a high level of evidence, e.g. National Institute for Health and Clinical Excellence (NICE), Grading of Recommendations Assessment, Development and Evaluation (GRADE), etc (38-41). However, we have allowed for 30% dropout in the sample size calculation to ensure that we have adequate power.

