iv) Screening: Only when there is measurable thickening in intima-media thickness ($>1.0\text{mm}$) can significant change be reliably detected as shown with 2 recent statin trials (42, 43) and a diet trial (22). Since it is estimated that between 30 to 50% of the non-diabetic population in our participants' age range have measurable arterial thickening (22, 44-46), we should be prepared to recruit and screen up to 3 times as many participants as we finally randomize to ensure measurable arterial thickening in our participants.

v) Sample size Calculation: We are using our previous power calculation (see below) for the present factorial design since we are advised that the final numbers required remain the same if there is no intended interaction between the two treatments. Using two-sample t-test, we would require 105 participants per treatment arm to detect a significant effect size of 106.5mm^3 (i.e. an end of treatment difference based on the expected relative cholesterol reduction in test vs. control, considering study length and dropout) with an end of treatment SD of 276mm^3 ($\alpha=0.05$, $1-\beta=0.80$)(47). However, since our final data will be analyzed by ANCOVA, we have used the ANCOVA sample size calculation to determine our final sample size. Due to the lack of r-values in the literature, and our expected recruitment of participants with preclinical vascular disease in a narrow range of screening arterial thickening, we anticipate only a modest degree of correlation

Name of Nominated Principal Applicant	(V21) September 2, 2022
[name]	
Full project title MRI – Enhanced Dietary Portfolio plus Exercise on Cardiovascular Risk	

Combined Study Protocol

between end and baseline values. We have therefore used a correlation of 0.6 in our ANCOVA sample size calculation which yields 67 participants required per arm (48). Therefore, assuming 30% dropout rate over 3 years (Please see Section 12B) XIV), we will need to randomize a minimum of 194 participants (81 per arm) for the proposed study. We will therefore screen and scan three times this number to ensure measurable arterial thickening, i.e. 576 theoretically eligible participants of whom one third will be randomized.

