12B) XIII. Are there likely to be any problems with compliance? Similar to our recent portfolio study, we expect on average participants to consume 41-46% of the recommended dietary components (adherence) which previously resulted in 13-14% LDL-C reductions (**JAMA 2011**) (4). This level of compliance is similar to the 52.5% adherence seen in our open-label unrandomized 1 year study (12). We anticipate that significant LDL-C reductions will be maintained over the 3 year study period. Therefore, to support adherence to the interventions over the duration of the study, optional activities will be offered to participants. These may include: 60-90-minute workshops, which will include 20-minute presentation of new research on foods encouraged on the respective diets, question and answer period, recipe tasting and discussion on modifications; cooking classes, which will be organized in collaboration with the Loblaws cooking school; quarterly info-graphic newsletters which will feature new research on specific foods included in the diets. We would also like to include a feedback survey to be collected from attendees at the end of each activity in order to assess how they were received and what can be improved upon for subsequent activities. Study participants will also be able to use a diet app, designed by our research team, to help with study compliance. It will include various resources including recipes, tip sheets, graphs summarizing their progress in following the dietary advice and personal messages to direct participants to resources to assist them in areas of

Name of Nominated Principal Applicant	(V21) September 2, 2022
[name]	
Full project title MRI – Enhanced Dietary Portfolio plus Exercise on Cardiovascular Risk	

Combined Study Protocol

difficulty. The app will be rolled-out over a few months in order to assess whether it has increased compliance and to review feedback on its use including addressing any technical issues. Metabolomics assessment will also occur at baseline and year one, to help identify objective biomarkers of specific foods consumed by the participants which is not prone to the same measurement and reporting errors of traditional self-report diet tools.

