a. 12B) XV. How many centres will be involved? Three recruitment sites will be involved: Institute of Nutraceuticals and Functional Foods, Laval University, Quebec; Healthy Heart Lipid Clinic, St. Paul's Hospital, Vancouver; and the Clinical Nutrition and Risk Factor Modification Centre, St Michael's Hospital or the David Naylor Building at the University of Toronto, and North York Family Health Team, North York General Hospital will be the recruitment clinics in Toronto. The MRI unit, Sunnybrook Health Science Centre, Toronto, Ontario, will be responsible for the interpretation of MRI scans. Robarts Institute, Western University, will be interpret and analyze screening US data. The Department of Biostatistics, McMaster University will oversee statistical aspects of the trial. The Nutritional Sciences Department, Faculty of Medicine, University of Toronto will also be involved in the assessment and quality control of recorded dietary data for all centres. We are adding an additional stress test clinic site, Toronto Cardiac Clinic because the stress test clinic at St. Michael's Hospital is not able to accommodate all of our research study patients because of the Covid-19 pandemic. Participants randomized (as opposed to screened) will be 98 at the Toronto site and 48 each at the other sites.

12B) XVI. What is the proposed type of analysis? An ANCOVA linear regression model will be used with the 3 year value as the outcome, treatment and sex as main effects and baseline as a covariate. In the intention-to-treat analysis, we will assume that data are multivariate, normally distributed and missing data are missing at random (MAR). For multiple imputations, the mean of 5 sets of generated data will be taken; this process will generate data for missing values, standard errors, and 95% confidence intervals [CI]. For example, using LDL-C

Name of Nominated Principal Applicant	(V21) September 2, 2022
[name]	
Full project title MRI – Enhanced Dietary Portfolio plus Exercise on Cardiovascular Risk	

Combined Study Protocol

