at 24 weeks in our recent study, the strongest predictors of missingness at 24 weeks were age ($\beta = 0.0454, P = .01$) and sex (women vs. men) ($\beta = -0.2807, P = .11$) (4), and these, along with the observed values, were used to inform the imputations. Site and diet assignment did not predict missingness in that study ($P \geq .16$) (4). As a sensitivity analysis, we will compare the results using the ITT with those of the completers-only. The 10-year Framingham CHD risk score will also be calculated (53) for this predominantly white cohort. Pearson correlation will be used to calculate the correlation coefficient between dietary adherence and change in maximum vessel wall volume (plaque volume).

12B) XVII. What is the proposed frequency of analyses? The imaging analyses will be made at baseline and year 3. Assessment of recruitment and retention will be made at 1y to inform further grant applications

12B) XVIII. Are there any planned subgroup analyses? No subgroup analyses are planned. However, we may conduct exploratory analyses by sex, site, or within groups meeting specified LDL-targets. Since we are not primarily powered for these analyses, we will treat these as secondary, exploratory analyses only.

12B) XIX. Has any pilot study been carried out using this design? A number of dietary portfolio studies (12) including the CIHR funded study of 6 months duration have now been completed (**JAMA 2011**) (4) demonstrating 13-14% LDL-C reductions with 40% adherence to all the recommended dietary components which are the same as those being tested in present study. Similarly, our CIHR funded low glycemic index study (**JAMA 2008**) (3) and our CIHR monounsaturated fat enriched portfolio study (**CMAJ 2010**) have also provided feedback (54). These studies have influenced the design of the present study in terms of power, magnitude of expected effect, and dropout rate, together with considerable feedback on participants' dietary preferences to facilitate overall adherence. The exercise protocol has been tested successfully in participants at high risk of CVD (55).

12C) TRIAL MANAGEMENT

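### The adherence analysis is fixed as an unadjusted Pearson correlation, within or across diets unstated, so a pooled version could reproduce the randomised diet contrast

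*Protocol*

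**What the plan says.** The sentence at issue closes the analysis paragraph of Protocol 12B) XVI: "Pearson correlation will be used to calculate the correlation coefficient between dietary adherence and change in maximum vessel wall volume". No covariate, subset of participants, hypothesis, target coefficient or sample size goes with it. It makes no causal claim.

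Earlier in the same section the main analysis is an ANCOVA on the 3-year value, with "treatment and sex as main effects and baseline as a covariate".

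Adherence is quantified once, in 12B) XIII: "we expect on average participants to consume 41-46% of the recommended dietary components". That range comes from the team's earlier portfolio trial. Table 1A, in 12B) II, lists component targets for Portfolio only. 12C) I speaks of adherence on the control diet in terms of whole grain cereals and gives no score. The design in 12B) I is a "randomized 2x2 factorial design with four experimental arms", so the two diets are compared at the margin.

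**The concern.** The protocol commits to a method here, so this is more than detail left for later. For one outcome, 12B) XVI uses treatment, sex and baseline in the main model and drops all three in the adherence analysis.

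Two consequences need separating.

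- **Diet arm.** If the correlation pools both diets and scores everyone on portfolio components, the portfolio group will tend to have higher adherence and, if the diet works as planned, a more favourable change in wall volume. The pooled coefficient then reflects the randomised contrast, whether or not adherence matters among people given the same advice.
- **Baseline.** Change from baseline is negatively correlated with baseline. Leaving baseline out adds noise. It adds bias only if adherence is itself related to baseline volume.

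What is at stake is how a supportive result is read. A significant negative r would look like evidence that closer adherence brings more regression, when it might only restate the trial's main comparison.

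**Working it through.** **Inputs from the Protocol, 12B) XI**
- Diet effect d = 106.5 mm³: "We have selected -106.5mm^3 as the effect size treatment difference at year 3".
- SD σ = 276 mm³: "with an end of treatment SD of 276mm^3".
- Baseline to end correlation ρ = 0.6: "We have therefore used a correlation of 0.6 in our ANCOVA sample size calculation which yields 67 participants required per arm".
- Dropout: "we have allowed for 30% dropout in the sample size calculation".
- Randomised: 194 (12B) XI), later enlarged to 260 (12B) XII (a)). Completers: 194 × 0.7 = 136 and 260 × 0.7 = 182.

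**Assumptions (not in the Protocol)**
- Adherence gap between diets, within-diet SD of adherence, and correlation of adherence with baseline volume. Ranges are shown.
- Equal numbers on each diet.

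**Step 1. Reproduce the plan's own figures.**
Two-sample n = 2 × [276 × (1.960 + 0.842) / 106.5]² = 105.4 per group (stated 105). ANCOVA: 105.4 × (1 − 0.6²) = 67.5 (stated 67). Both agree to rounding, so the inputs are read correctly.

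**Step 2. Properties of the change score.**
- SD of change = 276 × √(2 × (1 − 0.6)) = 246.9 mm³.
- Correlation of change with baseline = (0.6 − 1) / √0.8 = −0.447.
- Residual variance: 2(1 − 0.6) = 0.80 σ² for raw change, 1 − 0.6² = 0.64 σ² after baseline adjustment. This is a 20% reduction.

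**Step 3. Pooled r from the diet contrast alone.**
With no relation inside either diet, the pooled r is the product of two correlations, with a negative sign.
- Diet with change: 53.25 / √(246.9² + 53.25²) = 0.21. This is a ceiling on what the contrast alone can produce.
- Diet with adherence = (gap/2) / √(SD² + (gap/2)²).
  - Gap 35 (45% against 10%), SD 15: 17.5 / √(15² + 17.5²) = 0.76. Product 0.16.
  - Gap 15 (45% against 30%), SD 20: 7.5 / √(20² + 7.5²) = 0.35. Product 0.07.

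**Step 4. How often it would be significant (simulation, two-sided 5%, no within-diet relation, adherence unrelated to baseline).**

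| Completers | Gap (points) | SD | Mean pooled r | Significant |
|---|---|---|---|---|
| 136 | 0 | 15 | 0.00 | 6% |
| 136 | 20 | 15 | −0.12 | 27% |
| 136 | 33 | 15 | −0.16 | 45% |
| 182 | 0 | 15 | 0.00 | 5% |
| 182 | 15 | 20 | −0.07 | about 18% |
| 182 | 20 | 15 | −0.12 | 34% |
| 182 | 33 | 15 | −0.15 | 56% |
| 182 | 35 | 15 | −0.16 | about 60% |

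Within the portfolio diet alone, mean r is about 0 and the rate about 5% throughout.

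**Step 5. When baseline matters for bias.**
Let adherence correlate with baseline volume by an assumed +0.2. The within-diet r then becomes about −0.09. With −0.2 it becomes about +0.09. Rejection rates are 9% to 14%. With −0.2 it works against the diet contrast: at 136 completers and gap 33, the pooled r shrinks from −0.16 to −0.10. So it can hide an association as well as create one.

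**Step 6. Check of the repair.**
The partial correlation adjusted for diet and baseline has mean r about 0.00. Its rejection rate is about 4% to 6% in every scenario run, including those with adherence related to baseline.

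**The case against.** A reader might infer that the planned analysis does mix the diet contrast into the coefficient. The text does not establish that. It never says the diets are pooled, and a correlation run within the portfolio diet fits the sentence and carries no diet confounding. Nor does the Protocol fix one adherence scale for everyone. Portfolio targets exist for one diet only, and 12C) I describes control adherence in that diet's own terms. If each diet were scored against its own targets, the gap could be near zero and the pooled rejection rate nominal. This objection stands, and it makes the diet artefact conditional. It does not remove the point: the sentence names no subset, so an analyst could as readily pool, and the two readings behave very differently.

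A second tempting inference is that regression to the mean makes the correlation spurious. That needs an association between adherence and baseline volume, on which the Protocol is silent, and the sign could go either way. Only the precision loss is unconditional.

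Third, pooling rules and score construction are often left to a statistical analysis plan, which is not shown. That is fair for those details. But the method itself, a raw Pearson coefficient on a change score, is stated here, and it is weaker than the model used for the same outcome in the same section.

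Finally, this is one supportive sentence. It is not among the outcomes in 12B) VIII (a), and the Protocol does not call it a dose-response.

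**Conclusion.** The point holds in conditional form and is minor. The Protocol fixes an unadjusted correlation and leaves open whether it runs within or across diets.

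- **If pooled on a portfolio-based score:** the planned diet effect alone gives r of about −0.07 to −0.16, for assumed gaps of 15 to 35 points and SDs of 15 to 20. It is significant in roughly 18% to 60% of trials with 182 completers. With 136 completers it is significant in 27% to 45% for gaps of 20 to 33 points (SD 15).
- **If run within one diet, or with no gap:** no such artefact.
- **Baseline:** its omission leaves residual variance at 0.80 instead of 0.64 of σ² in any case. It biases r only if adherence is related to baseline volume.

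The effect, SD, correlation and dropout are the Protocol's. The adherence figures are assumptions, so the percentages show a possible size and are not predictions. The documents do not support a claim that the result will be spurious. The primary test and the sample size are untouched.

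**What to change.** Replace the sentence in 12B) XVI with a regression of year-3 vessel wall volume on adherence, either within each diet or with diet in the model, adjusted for baseline volume and sex as in the main model. With baseline included, using the year-3 value or the change gives the same adherence coefficient. Report the partial correlation from that model. State how adherence is scored on each diet, and label the result exploratory and non-randomised. Adding exercise arm and centre is optional: exercise is randomised in a factorial with diet, and centre is not in the stated main model.

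Cost: one rewritten sentence and a regression in place of a correlation. Every variable is already held, so this is a free improvement.

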The steering committee and the Data Safety Monitoring Committee (DSMC) will be modeled on current practice for our CIHR funded diabetes trial. The steering committee will be made up of the site PIs who will discuss initially monthly by conference call problems as they arise, especially recruitment goals and later with quarterly conference calls. For specific issues, e.g. MRI, etc, those responsible (Please see above) will be involved. Adverse events will be reviewed by a physician independent of the study. The DSMC will involve physicians from other centres experienced in clinical trials (our current CIHR diabetes trial DSMC members will be

Name of Nominated Principal Applicant	(V21) September 2, 2022
[name]	

Full project title

MRI – Enhanced Dietary Portfolio plus Exercise on Cardiovascular Risk

Combined Study Protocol

approached first for membership) who will review serious adverse events immediately and minor events at 6 month intervals.

OTHER ISSUES

Details of risks to the safety of participants involved in the trial. We see little risk associated with the dietary components of the trial. The foods to be used are available for purchase in supermarkets except for a psyllium-enriched oatbran bread which we have had provided by local bakers in our previous studies (JAMA 2011) (1). Those with food allergies to the dietary components will not be recruited. The exercise program is a structured program. The work intensity corresponds to brisk walking. Therefore, the risks of our program are very low, even among high risk individuals. For instance, we have had no recurrent CHD events experienced by our high risk participants who were exposed to this intervention for one year. We are therefore fully confident in the wide applicability of our physical activity/moderate endurance exercise prescription as it essentially corresponds to current public health recommendations. Furthermore, in addition to the 3-monthly visits, participants will have access to the kinesiologist (phone, e-mail, etc) to obtain further support/assistance if need be.

Health Economics: The proposed first trial is relatively small to allow detailed assessment of health economics. However, it will be possible to obtain an assessment of the cost of dietary change from participants' food records and from participants' weekly food costs before and during the diet and relate these costs to the LDL-C reduction. The cost of dietary LDL-C reduction can in turn be compared with the cost of statin usage for a similar LDL-C reduction. Meaningful economic measures will be derived from a future large hard endpoint multi-centre trial.

Quality of Life: The Medical Outcomes Study 36-Item Short Form Questionnaire (SF-36) will be administered pre-study and at Year 3. We have also included taste, satiety and sustainability (preparedness to continue on the diet) questions in the protocol which we believe will go some way to addressing this issue. The SF-36 has been used in numerous clinical studies (56, 57) with very good psychometric properties, and provides a comprehensive and subject friendly tool to assess quality of life.

Cognitive Assessment: The Montreal Cognitive Assessment (MoCA) (version 7.1 original version) will be administered at months 0, 12, 24 and 36. This tool measures different cognitive domains such as attention, concentration, memory, language etc. (ref. Z. Nasreddine MD; www.mocatest.org). **The Mild Behavioural Impairment scale (MBI-C) will be administered at months 0, 12, 24, and 36 months.** The MBI-C is designed to detect behavioural pre-dementia at-risk states with a high level of sensitivity and specificity (ref: Ismail, Z. <https://mbitest.org/>). The MBI-C is a free validated rating scale consisting of 34 questions, which takes around 10-15 minutes to complete and is designed to be completed by either participant, close informant or clinician at clinic or over the phone.

Age: Women will be post-menopausal. The lower limit on age for men is of little significance since men in our subject pool are predominately in the 50y plus age range. We have no upper limit providing volunteers are in good health.

Consumer Involvement in Trial Development: We have not formally asked our previous or potential future participants to assess our current plans but have used the comments made by participants in our recent dietary portfolio and glycemic index CIHR funded trials. Their

Name of Nominated Principal Applicant	(V21) September 2, 2022
[name]	

Full project title

MRI – Enhanced Dietary Portfolio plus Exercise on Cardiovascular Risk

Combined Study Protocol

suggestions are reflected in our use of a positive control diet rather than simply the standard of care. The control is both high fibre and a DASH-type diet with additional potential benefits on lipids and blood pressure.

Genetic Testing: This aspect of the study will be optional.

Objective: To determine whether there are differences between individuals in their response to exercise and dietary change, e.g. changes in plant oil intake, low versus high glycemic index foods or a lower carbohydrate diet.

Background

There is considerable interest in the scientific community to study how genes may influence response to diet / exercise. We know for example that carriers of the apo E3 / E4 allele tend to show better cholesterol lowering responses to soy in terms of LDL-C reduction (Gaddi et al. AJCN 1991;53 (5):1191-96) and also better responses to viscous fiber (Jenkins DJA, Hegele RA, et.al. Metabolism 1993;42 (5):585-93). We have recently found that equol producers (from the soy isoflavone, genestein) also appear to respond to soy by raising HDL-C, suggesting that in this group soy may be particularly cardio protective. In terms of taste our diets tend to be bland containing lower salt and also less sugar. The genes controlling these tastes may therefore determine intake and adherence to therapeutic diets (Dias AG et. al. Chem Senses. 2013 Feb; 38(2):137-45, Eny KM et al. Physiol Genomics. 2008;33(3):355-60, Garcia Bailo et al. OMICS. 2009;13(1):69-80). A variant in the APOA2 gene has also been shown to modify the relationship between saturated fat intake and BMI (Corella et al. Arch Intern Med. 2009;169(20):1897-906. These are a few examples of why comprehensive genetic analysis, due to the implication of a growing number of genes of interest, would be helpful. We will, however limit our analyses to specific genes currently known to affect dietary response. Generally, the effect of genes on diet is very modest and usually requires significant numbers of people to detect the difference. It therefore has very limited clinical relevance. We therefore plan to pool data from across our studies (typically 140-340 participants per study) which have the same high fiber treatment for the control groups, and the dietary portfolio in the test groups, to provide the larger numbers required to detect a difference if one exists. A bio-bank will be established for the proper storage and management of these samples

We hope to make our initial findings known to participants at the end of the study, especially if we discover specific groups for which certain types of dietary advice may prove advantageous. Genetic testing results are solely for use in this study and will not be shared with any third parties (i.e. insurance companies or the hospital)

Analyses

The DNA will be extracted from “buffy coat” of white blood cells obtained after plasma has been removed from citrated blood samples (blue tops) drawn at week 0 or any time point during the main study. Therefore, no additional blood samples will be required for this study.

The genes of interest will include those related to the effectiveness of dietary change on blood glucose, cholesterol and associated measurements including blood pressure, taste preference,

Name of Nominated Principal Applicant	(V21) September 2, 2022
[name]	
Full project title MRI – Enhanced Dietary Portfolio plus Exercise on Cardiovascular Risk	

Combined Study Protocol

compliance (dopamine receptor polymorphisms) and other related genes which may influence response to diet.

Incidental findings

An incidental finding is a finding concerning an individual research participant that has potential health or reproductive importance and is discovered in the course of conducting research but is beyond the aims of the study.

(Managing Incidental Findings in Human Subjects Research: Analysis and Recommendations. Wolf SM et al J Law Med Ethics. 2008; 36(2):219-48)

Any incidental findings (as defined above) obtained from screening or during the course of the main study from laboratory tests, ultrasound or MRI images will be provided to the family physician for further investigation. The participant will be notified in reassuring terms and advised to follow-up with their family physician. Furthermore, if from the Carotid ultrasound a participant is found to have a luminal narrowing greater than 50% the individual will have the option of referral to a vascular surgeon for further assessment. However, in a similar cohort of 160 patients being screened by ultrasound none were found to have an incidental stenosis of this magnitude.

In this sub-study, if genes identified have clinical implications the advice of experts in that particular field will be sought to arrange appropriate counseling for the participant. The family physician's involvement would be sought if the participant consents to it. However, the chances of incidental findings are limited since only specific genes known to affect dietary response will be studied.

Banking of Samples: Blood samples (de-identified) will be stored at the University of Toronto (at the Medical Science Building or the MaRS centre) until all planned analyses have been undertaken-usually about 3 to 5 years. Optional longer-term banking will be made available to all participants for storage periods of 25 years after study completion to allow for use in future secondary analyses in relation to the objectives of the current research project. At the end of each storage period, samples will be destroyed by autoclaving.

We are currently investigating the process of setting up a Biobank to efficiently and securely store and manage these samples; the necessary application will be sent to the St. Michael's REB once the project proposal is drawn up.

Presently the use and ultimate destruction of these samples will be the responsibility of the following investigators, individually or collectively: [name], [name] and [name]. However, detailed information on the organization and management will be in the biobank proposal that will be submitted to the REB in the near future.

International Collaboration: None.

Patient Information Sheet: To be developed after grant review.

Name of Nominated Principal Applicant	(V21) September 2, 2022
[name]	
Full project title	
MRI – Enhanced Dietary Portfolio plus Exercise on Cardiovascular Risk	

Combined Study Protocol

Industrial Partners: If awarded, Loblaw Ltd. and Unilever have committed to provide unrestricted funds of \$360,000 and \$50,000 respectively. (Please see Appendix 7 for letters of support)

Trial Significance: If this trial demonstrates a 10% or better estimated CHD risk reduction based on the primary (anatomical) outcome (MRI Vessel Wall Volume), it will both encourage the use of this combined dietary and exercise strategy in clinical practice and provide the necessary stimulus for an international hard endpoint (cardiovascular events) trial for which the trialists' network will form the nucleus.

References

